To our knowledge, so far, no clinical trial has been performed prospectively to quantify the viral reservoir in order to identify patients in whom cART could safely be interrupted. We will therefore prospectively evaluate about 640 cART treated HIV-1 positive patients in order to select a subgroup of individuals with extremely low HIV reservoirs, defined as an undetectable total HIV DNA and cell-associated HIV RNA (see section 5.1.3 for details) (first strategic goal). In those patients harboring low HIV reservoir, an analytical treatment interruption will be proposed (second strategic goal). Clinical and laboratory parameters (including VOA at baseline) of ensuing controllers and non-controllers (PTC vs. non-PTC) should allow us to identify predictors of functional cure after ATI (third strategic goal).

The innovative approach taken in this trial should help to take decisions on interrupting cART in future HIV cure strategies and lead to the identification of clinical and laboratory parameters correlating with PTC.

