# **3. STUDY OBJECTIVES**

The project hypothesis is that treatment interruption (TI) of longstanding combined antiretroviral therapy in participants with a very low proviral reservoir results in "functional cure".

The **primary objective** is to determine the proportion of post treatment controllers (PTC) i.e. patients under cART with low baseline peripheral blood proviral DNA that will show sustained viral suppression at 48 weeks post TI.

The secondary objectives are:

Confirmation of the safety of a TI strategy in selected HIV patients

Assessment of the viral reservoir magnitude prior and after TI

Assessment of viral and host dynamics in those participants with viral rebound post TI. The **exploratory objective** is:

Identification of predictors (clinical and/or laboratory) of PTC phenotype

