### 5.1.6 STUDY VISITS (48 WEEKS)

Following treatment interruption, study visits will be planned at week 2, 4, 6, 8, 10, 12, 16, 20, 24, 32, 40 and 48.

The evaluations performed at each study visit are detailed in the table 2 above. Beside the described information thorough counselling on the risk of transmitting HIV will be provided at each study visit.

At each time point PBMC from an extra sample (Three EDTA tubes of 9ml) will be stored according to the sample storage procedure. These samples will be used to measure the dynamic of usRNA during and after treatment interruption. The last study visit (either at week 48 or at viral rebound) will coincide with the first visit of the post-intervention phase.

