### 5.1.7 Study discontinuation

The study will be discontinued and cART will be restarted whenever:

- A pVL increase above 1,000 copies/ml at two consecutive time points during ATI, at least 3 days apart

- A single viral load increase > 10.000 copies

- CD4+ T-cell count drops below  $350/\mu$ l at two consecutive measurements at least 2 weeks apart or a drop of more than 50% compared to baseline

- Any new significant clinical condition (linked to HIV or not) is documented

- A new sexually transmitted infection is diagnosed

- A woman would become pregnant despite the recommended anti-conception

- A participant decides to withdraw from trial

As soon as such event is noticed, the participant will be contacted urgently by phone to come back earlier in order to perform an End Of Study visit and restart cART without delay. If a participant was in mono-or bitherapy before treatment interruption, it will be strongly advised to restart with tritherapy upon viral rebound.

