# 5.1.8 POST-INTERVENTION PHASE (FROM WEEK 48 OR UPON VIRAL REBOUND FOR A DURATION OF 12 WEEKS).

The post-intervention phase will start either at week 48 for the post-treatment controllers (undetectable viral load without treatment) or at time of cART re-initiation for the patients with viral rebound. During this period of 12 weeks, additional evaluation of the viral reservoir will be performed as well as an assessment of the efficacy of the cART restarted among participant with viral rebound.

The assessments performed during the post-intervention phase are resumed in the flowchart below.

Procedure	EOS*	W4	W12	Comments
Safety				
Targeted Phys Exam.	Х	Х	X	
Vital Signs	Х	Х	X	
Concom. Medications	Х	Х	X	
SAE assessement	Х	Х	X	
AE assessement	Х	Х	X	
cART history	Х	Х	Х	
Laboratory Tests				
Plasma Viral Load	Х	Х	X	
CD4 Cell count	Х		X	
Resistance Test	Х	(X)	(X)	(if indicated)
Hemoglobin	Х	(X)	(X)	(if indicated)
ANC	Х	(X)	(X)	(if indicated)
Platelet	Х	(X)	(X)	(if indicated)
Ureum/Creatinin	Х	(X)	(X)	(if indicated)
AST/ALT	Х	(X)	(X)	(if indicated)
Pregnancy test	Х		Х	
Reservoir Assessment				
Tot. HIV DNA	Х		X	
Us RNA	Х		X	
Proviral DNA	Х		X	
Sample storage	Х		Х	

 Table 3: Flowchart of the post-intervention phase

EOS: end Of Study

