### 8.3.6 Multiplicity and Missing Data

Complete-case analyses will be performed.

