This is a single arm multi-centric non-randomized (prospective) clinical trial. The study will be divided in two parts. The first one will aim at quantifying the HIV reservoir in a large group of patients under ART with strictly predefined inclusion and exclusion criteria. The second step encompasses an analytical treatment interruption among participants with the lowest viral reservoir.

2.2. Study objectives and Hypotheses

Primary Objective

The primary objective is to determine the proportion of post treatment controllers (PTC) (i.e. patients under cART with low baseline peripheral blood proviral DNA that will show sustained viral suppression at 48 weeks post treatment interruption (TI).

Secondary Objectives

a. To confirm the safety of a TI strategy in selected HIV patients

b. To assess the viral reservoir magnitude prior, during and after TI

c. To assess the viral and host dynamics in those participants with viral rebound post TI.

Exploratory Objective

- a. The identification of predictors (clinical and/or laboratory) of PTC phenotype.
- b. The identification of predictors for viral rebound over time.

2.3. Variables of interest

Primary: The proportion of participants with plasma viral load (pVL) below the lower limit of detection (< 50 HIV RNA copies/ml plasma) 48 weeks following interruption of ART.

Secondary:

- The numbers and percentages of AE's and SAE's during the whole study period.
- Viral reservoir (total HIV-1 DNA) and viral transcription (total HIV-1 cellassociated RNA) measurements at every visit between baseline (just before TI) until viral rebound and 12 weeks after viral rebound.
- Repeated pVL measurements.

Exploratory: Potential clinical and/or laboratory variables, such as demographic and epidemiological data, medical history (past and current), vital parameters, ultrasensitive HIV viral load, CD4 T cell count and laboratory test data (e.g. hemoglobin, ANC, platelets, creatinine, AST & ALT), viral reservoir (quantitative viral outgrowth measurement) and viral release measurements (spontaneous and stimulated) at baseline.

3. Description of study population

3.1. Analysis populations

The statistical analyses will be performed on all participants enrolled in the study and who met all inclusion and exclusion criteria. Complete case analysis will be performed for all statistical analyses.

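### Complete-case analysis of the week-48 proportion, read literally, removes participants who rebound and restart ART, although the planned 2 to 5 of 32 needs them in the denominator

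*SAP*

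**What the plan says.** SAP 3.1 sets one rule for incomplete data: "Complete case analysis will be performed for all statistical analyses". Protocol 8.3.6 says the same: "Complete-case analyses will be performed". Neither makes an exception for the primary endpoint. That endpoint is a single measurement, pVL below 50 copies/ml 48 weeks after interruption (Protocol 3.1, 8.2 and 8.3.3; SAP 2.3 and 4.1).

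Protocol 5.1.7 ends the study and restarts cART on several grounds. One is "A pVL increase above 1,000 copies/ml at two consecutive time points during ATI, at least 3 days apart"; another is a single value above 10,000. Participants who meet a criterion do not go on to week 48. Protocol 5.1.6 states: "The last study visit (either at week 48 or at viral rebound) will coincide with the first visit of the post-intervention phase". Table 3 then schedules pVL at that visit and 4 and 12 weeks later. Protocol 4.5 also lists meeting the rebound criteria among the reasons for withdrawing a participant, and SAP 3.2 has no discontinuation category for rebound.

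The apparent intent is that rebounders count as failures. The objective in Protocol 3 concerns patients "that will show sustained viral suppression at 48 weeks post TI". Protocol 1.2 says that the parameters "of ensuing controllers and non-controllers (PTC vs. non-PTC) should allow us to identify predictors of functional cure after ATI". Protocol 5.1.8 starts the last phase at week 48 for "post-treatment controllers (undetectable viral load without treatment) or at time of cART re-initiation for the patients with viral rebound". Protocol 4.3 expects 2 to 5 controllers among 32, Protocol 8.3.1 analyses everyone enrolled, and SAP Example Table 6 has a column for non-controllers.

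**The concern.** Whether the week-48 value exists depends on the outcome. Controllers reach week 48; most participants who rebound leave before it, by design. Protocol 11.1 expects rebound in a majority. If a complete case means a participant with a week-48 pVL, the analysis removes failures from the denominator and keeps every success. The bias is upward, towards the study hypothesis, in a single-arm trial with no comparator to expose it.

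There is a second, smaller gap. The endpoint sentence does not require the participant to be off treatment; that condition appears only in Protocol 5.1.8. A participant who restarted ART and is suppressed on it near week 48 would satisfy the wording.

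The descriptive proportions at weeks 4, 6 and 8 in SAP 4.1 have the same problem. Week 2 is essentially unaffected, because it is the first visit after interruption.

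**Working it through.** **Inputs.** N = 32 (Protocol 4.3, 8.4). Controllers: 5 to 15%, taken as 2 to 5 of 32 (Protocol 4.3). 95% Wilson interval (SAP 4.1). Visit window ±7 days (Protocol 5.1). The documents do not give the share of non-controllers without a week-48 pVL; the shares below are assumptions.

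**Formula.** With p = k/n and z = 1.96, the limits are [p + z²/(2n) ± z·√(p(1−p)/n + z²/(4n²))] / (1 + z²/n).

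**Step 1: reproduce the plan's figure.**
- 2/32 = 6.3%, interval 1.7 to 20.1, width 18.4 points.
- 5/32 = 15.6%, interval 6.9 to 31.8, width 24.9 points.

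These match the 18 to 25 points in Protocol 8.4. The stated precision therefore assumes that all 32 participants, rebounders included, are in the denominator.

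**Step 2: can a rebounder have a week-48 value?** After restart at week R, pVL is scheduled at R, R+4 and R+12. For restart at a scheduled visit from week 2 to week 40, none of these falls in weeks 47 to 49. The latest cases are R = 32 (weeks 36 and 44) and R = 40 (weeks 44 and 52). Allowing ±1 week does not change this.

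Restart between visits is plausible, because once a criterion is noticed "the participant will be contacted urgently by phone to come back earlier". Restart in weeks 34 to 38 (through R+12) or weeks 42 to 46 (through R+4) can give a pVL in weeks 47 to 49, but that value is taken on ART. Likewise, restart at the week-2 or week-4 visit puts the R+4 value, on ART, at study week 6 or 8.

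**Step 3: literal complete case.** There are 30 non-controllers if 2 control and 27 if 5 control. Numbers dropped are rounded down.

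| Non-controllers dropped (assumed) | 2 controllers | 5 controllers |
|---|---|---|
| 0% | 2/32 = 6.3% (1.7–20.1) | 5/32 = 15.6% (6.9–31.8) |
| 25% (7 of 30; 6 of 27) | 2/25 = 8.0% (2.2–25.0) | 5/26 = 19.2% (8.5–37.9) |
| 50% (15; 13) | 2/17 = 11.8% (3.3–34.3) | 5/19 = 26.3% (11.8–48.8) |
| 75% (22; 20) | 2/10 = 20.0% (5.7–51.0) | 5/12 = 41.7% (19.3–68.0) |

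At 50% the widths are 31 and 37 points.

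An anchor from the protocol: the smallest possible majority is 17 of 32. If all 17 restart and are dropped, the results are 2/15 = 13.3% (3.7–37.9) and 5/15 = 33.3% (15.2–58.3), each 32/15 = 2.1 times the intended figure.

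Dropping every non-controller (2/2 or 5/5) is only the extreme bound. Viraemia between 50 and 1,000 copies/ml meets no virological restart criterion and can be observed as failure at week 48.

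**Step 4: on-ART suppression counted as success.** One such participant moves 2/32 to 3/32 = 9.4% (3.2–24.2), or 5/32 to 6/32 = 18.8% (8.9–35.3).

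**The case against.** The strongest reply is that complete case is a rule for missing data and rebound is not missing data. A participant whose rebound ended the interruption has a known outcome: suppression was not sustained. On that reading the plan already gives x/32. The literal reading would also take most of the non-controllers out of Example Table 6 and undermine the planned Fisher tests. This is very probably what the authors mean. But no analysis sentence says it, the only written rule points the other way, and Protocol 4.5 treats meeting the rebound criteria as a ground for withdrawal.

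Four further points deserve weight:

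- **The size is assumed.** This is correct, and the table is labelled accordingly. The 17-of-32 case also implies 10 to 13 participants who are neither controllers nor dropped. It shows the effect of the smallest majority and is not a forecast.
- **The on-ART success needs a chain of events:** restart between visits, re-suppression, and a post-intervention value assigned to week 48. This is a minor route, but a few words close it.
- **A reduced denominator would be visible,** because Example Table 3 shows n/N and discontinuations are tabulated by reason. The exploratory Kaplan-Meier analysis would also count rebounders as events. Visibility helps a reader but does not correct the primary estimate.
- **Counting every restart as non-control is a choice,** since some participants may restart while suppressed. It agrees with the off-treatment description in Protocol 5.1.8, but it should be stated openly.

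**Conclusion.** The concern holds and should be settled before database lock. The only stated missing-data rule, applied literally to a week-48 measurement, excludes participants because they failed. It contradicts the protocol's own expectation of 2 to 5 of 32 and the width of 18 to 25 points, which needs all 32.

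The direction of the bias is certain under that reading; its size is not. With 25% to 75% of non-controllers dropped, the estimate rises from 6.3% to between 8.0% and 20.0% with two controllers, and from 15.6% to between 19.2% and 41.7% with five. If the analyst codes rebound as failure there is no bias, but the primary result should not depend on an unwritten decision.

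**What to change.** Add to SAP 3.1 and 4.1, and align Protocol 8.3.3 and 8.3.6:

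> The denominator is all participants in the analysis population who interrupted ART. Success is pVL below 50 copies/ml at week 48 without ART having been restarted. Viral rebound meeting the protocol's existing discontinuation criteria, or ART restart, before week 48 is an observed non-control outcome and is not treated as missing.

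Apply the same rule to the week 4, 6 and 8 proportions. State also whether the SAP 3.1 restriction to participants who met all eligibility criteria is kept, since Protocol 8.3.1 says all enrolled.

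As a separate, optional choice, count participants who leave while suppressed, or whose week-48 status is unknown, as non-controllers in the primary analysis. Add a best-case/worst-case sensitivity analysis for them and for those who restarted while suppressed. With three such participants (assumed), the worst case stays at 2/32 to 5/32, and the best case is 5/32 = 15.6% to 8/32 = 25.0% (13.3–42.1).

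The cost is three sentences for the core rule. No new data are needed and clinical management does not change. The protocol text can follow later; if the change counts as substantial, Protocol 11.3 requires approval by all the bodies that approved the original. The downside is slight conservatism, because participants who restart while suppressed for a non-virological reason count as non-controllers. The optional sensitivity analysis would show by how much.

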3.2. Patient accounting

The numbers of participants screened, enrolled and excluded will be presented. Excluded participants will be summarized by reason for exclusion in a CONSORT flow diagram by the PI.

All patients who conform to all inclusion and exclusion criteria and are enrolled into the study will be tabulated. The number of patients discontinued will be tabulated by reason for study discontinuation (Completed the study, Lost to Follow Up, Withdrawal of Consent, Discontinuation of drug for Safety or Other Reasons, Death, Other) (Example Table 1). This information will also be described separately in a CONSORT flow diagram.

3.3. Description of study population

Patients will be described with respect to baseline characteristics for each of the two stages of the study separately. The description will be in terms of medians and interquartile ranges for continuous characteristics and using counts and percentages for categorical characteristics (Example Tables 2). The clinical importance of any imbalance will be noted, though statistical tests of significance will not be undertaken.

4. Statistical Methods

4.1. Primary Objective

The primary objective will be assessed by estimating the proportion of participants with undetectable viral load (<50 HIV RNA copies/ml plasma) 48 weeks after interruption of ART. A 95% CI for the proportion will be calculated using Wilson's score method (Example Table 3). Respective proportions at different time points (week 2, 4, 6 and 8) will be also calculated for descriptive purposes.

4.2. Secondary Objectives

Adverse events (AEs) will be coded using the Medical Dictionary for Regulatory Activities (MEDDRA) and will be reported based on MEDDRA preferred terms and body systems. All AEs will be analyzed based on counts of patients with a specific category and not on counts of individual adverse events. The relationship between AEs and ARV interruption is determined by the investigator and categorized as "drugrelated" if unlikely, possibly, likely or definitely related to treatment interruption. All AEs definitely unrelated to intervention will also be used to examine the relationship between AEs and intervention.

All AEs and all serious AEs from the beginning of treatment interruption until the end of the study (end of follow-up period) are reported. AE counts will be summarized for the whole study period (treatment interruption and follow-up period). Counts (%) of patients with AEs, drug-related AEs and serious AEs will be presented by Meddra body system and preferred term together with a 95% Wilson confidence interval (Example Table 4 and 5).

Reservoir replenishment and HIV viral load kinetics following ART interruption will be summarized in terms of medians and interquartile ranges (Example Table 3). No formal statistical testing will be done in these results. If present, pVL rebound will be represented graphically with a spaghetti plot. Furthermore, the measurements over time of viral load rebound and viral reservoir will be presented graphically for every patient included in the study (one line for every patient over time).

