### Definition of an Adverse Event

An Adverse Event (AE) is generally described as any untoward medical occurrence in a subject or clinical investigation subject administered a pharmaceutical product and that does not necessarily have a causal relationship with this treatment. An AE can therefore be any unfavorable and unintended sign (including an abnormal laboratory finding), symptom, or disease temporally associated with the use of a medicinal (investigational) product, whether or not related to the medicinal (investigational) product.

However, this definition does not entirely fit the purpose of this study, because we will not assess a pharmaceutical product. Therefore, we will consider the intervention (=interruption antiviral treatment) as the pharmaceutical product under investigation and will adapt the definition accordingly:

An Adverse Event (AE) is generally described as any untoward medical occurrence in a subject or clinical investigation subject with treatment interruption and that does not necessarily have a causal relationship with the treatment interruption. An AE can therefore be any unfavorable and unintended sign (including an abnormal laboratory finding), symptom, or disease temporally associated with the treatment interruption, whether or not related to the treatment interruption.

Once treatment interruption has started, until the end of study, clinic staff will enquire about common possible side effects based on the "division of AIDS table for grading the severity of adverse events (see annex)" and will ascertain the occurrence of any adverse events since the last visit. All of them, including clinically significant laboratory abnormalities, will be recorded in the electronic Case Record Form (eCRF) and categorized in terms of severity, relationship to ARV interruption, outcome and seriousness, throughout the study duration. Episodes of viral acute syndrome, possible events of special interest, all serious adverse events (SAEs) and all the events leading to participants' withdrawal from the study will be monthly communicated to the Scientific Advisory Board.

All the events will be followed up till resolution, except those at the final end of study (=end of follow-up period).

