### Assessment of causality

The investigator will assess the relationship between the ARV interruption and the occurrence of each AE/SAE. A list of expected adverse event is given. In addition, the investigator will use clinical judgement to determine the possible relationship of other (not expected) events.

The relationship of an adverse event to ARV interruption is to be assessed according to the following definitions and can only be done by the study physician:

- 1. **Definitely unrelated**: Reserved for those events which cannot be even remotely related to ARV interruption (e.g. injury caused by a third party).
- 2. Unlikely: There is no reasonable temporal association between the ARV interruption and the AE, the AE is not expected (according to a pre-defined list) and the event could have been linked to other known reasons.
- 3. **Possible**: The suspected AE may or may not follow a reasonable temporal sequence from ARV interruption but It is not fully unexpected but it could be linked to other known reasons.
- 4. Likely: The suspected adverse event follows a reasonable temporal sequence from ARV interruption. Either it is expected (according to based on the "division of AIDS table for grading the severity of adverse events) or it is likely caused by ARV interruption in the investigator's judgment.
- 5. **Definitely related**: Reserved for those events which have no uncertainty in their relationship to ARVs interruption.

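### SAP 4.2 counts adverse events rated *unlikely* as related to treatment interruption without giving a reason, and no planned table can separate them out

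*SAP*

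**What the plan says.** Protocol 7.1 (Assessment of causality) has the investigator rate every event on five levels: definitely unrelated, unlikely, possible, likely and definitely related. Three of the definitions matter here:

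- *Definitely unrelated*: "Reserved for those events which cannot be even remotely related to ARV interruption", with injury by a third party as the example.
- *Unlikely*: "There is no reasonable temporal association between the ARV interruption and the AE, the AE is not expected", and the event could have been linked to other known causes.
- *Possible*: the timing may or may not fit, but "It is not fully unexpected but it could be linked to other known reasons".

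The protocol sets no cut-point between related and unrelated.

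SAP 4.2 sets one. An AE is drug-related "if unlikely, possibly, likely or definitely related to treatment interruption". It adds: "All AEs definitely unrelated to intervention will also be used to examine the relationship between AEs and intervention". AEs are counted by patient, not by event.

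The planned tables are Example Table 4 (body system and preferred term), with further versions for drug-related, serious and serious drug-related AEs, and Example Table 5. Table 5's title refers to causality classification, but it has four rows: any AE, any intervention-related AE, any SAE, any intervention-related SAE.

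**The concern.** The first secondary objective in SAP 2.2 is "To confirm the safety of a TI strategy in selected HIV patients". The trial has one arm, so no control rate puts the related-AE and related-SAE rates in context, and the reader depends on what *related* means.

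Under SAP 4.2 it means everything except a deliberately narrow residual category. Because *definitely unrelated* is kept for events with no conceivable link, the related rate can drift towards the any-AE rate and say little more than that rate does. The group labelled related then includes events that the investigator judged to lack a reasonable time link. If the tables allowed the reader to remove those events this would hardly matter, but they do not.

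There are two smaller points. The sentence on definitely unrelated AEs names neither a method nor a table. The same group also carries two labels, drug-related in SAP 4.2 and the Table 4 note, and intervention-related in Table 5.

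**Working it through.** **What each planned table can show.** Count each patient at his or her highest causality rating.

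| Table | What it gives | Separates *unlikely* from possible, likely or definite? |
|---|---|---|
| Table 5, any AE or SAE | all five levels pooled | no |
| Table 5, related AE or SAE | upper four levels pooled | no |
| Table 5, any minus related | patients at *definitely unrelated* only | no |
| Table 4, drug-related and serious drug-related versions | upper four levels pooled, by preferred term | no |

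**Inputs.** N = 32 is the planned number stopping treatment (Protocol 8.4). N = 45 is the number expected to qualify (Protocol 4.3, Step 4). N = 16 is an assumption, for a smaller trial. The documents give no expected AE counts and no causality split, so every AE count below is an assumption.

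**Weight of one participant.** Each participant whose highest rating is *unlikely* raises the related rate by 1/N:

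- 1/32 = 3.1 points
- 1/45 = 2.2 points
- 1/16 = 6.3 points

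**Wilson interval.** With p = x/n and z = 1.96, the centre is (p + z²/2n)/(1 + z²/n) and the half-width is z·√(p(1−p)/n + z²/4n²)/(1 + z²/n). The plan states no AE figure to reproduce. As a check on the formula, 2/32 and 5/32 give widths of 18.4 and 24.9 points, which agree with the 18 and 25 in Protocol 8.4.

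**What a reader could infer from Table 5.** Assume any AE in 20/32 and related AE in 12/32.

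- Patients with only definitely unrelated events: 20 − 12 = 8.
- Related rate: 12/32 = 37.5%. The centre is 38.840% and the half-width 15.906%, so the interval is 22.9 to 54.7%.
- The number rated possible or stronger is known only to lie between 0 and 12:

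| Possible or stronger | Rate | 95% Wilson interval |
|---|---|---|
| 0/32 | 0.0% | 0.0 to 10.7 |
| 4/32 | 12.5% | 5.0 to 28.1 |
| 8/32 | 25.0% | 13.3 to 42.1 |
| 12/32 | 37.5% | 22.9 to 54.7 |

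All four rows are consistent with the same printed Table 5.

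**SAEs.** A reported related SAE in 1/32 = 3.1% (0.6 to 15.7) is compatible with 0/32 (0.0 to 10.7) rated possible or stronger.

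**The case against.** The strongest reply is that this is an explicit, pre-specified and cautious convention. It breaches no protocol rule, and it can over-count related events but cannot hide one. The protocol's own wording gives it some support. The SAP draws its line exactly where the protocol rules out any relation. Because *possible* requires that an event be not wholly unexpected, an unexpected event with plausible timing, not judged likely to be caused by the interruption, fits neither *possible* nor *unlikely* cleanly and might be rated *unlikely*. Pooling keeps such an event in the related count. All of this stands, and it is why either grouping can be kept.

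It is also true that Protocol 8.3.4 bases safety on AE and SAE percentages, which depend on no causality cut-point, that no test or threshold is attached, and that SAE oversight is unaffected. The protocol treats the interruption as if it were the product ("we will consider the intervention (=interruption antiviral treatment) as the pharmaceutical product under investigation"), so the two labels very probably mean the same thing. These facts limit the severity.

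A further reply is that the shells are only examples and that the SAP's introduction allows additional analyses. A split is therefore permitted, but it is not planned, and the decision to show it would be made after the data are seen. None of these replies shows that the planned tables can separate *unlikely* from the stronger ratings.

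**Conclusion.** The concern holds, as a minor one. SAP 4.2 counts *unlikely* events as related without a stated reason, and none of the planned tables lets a reader undo that. The related-AE and related-SAE rates, and the preferred-term counts in the drug-related versions of Table 4, can only be equal to or higher than under a possible/likely/definite grouping.

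The actual size is unknown and could be zero, since it depends on how many participants have *unlikely* as their highest rating. The scale of 3.1 points per participant rests on the planned N of 32, and the 0 to 37.5% range rests on the assumed counts. Confidence is high on what the documents say. The reading of Table 5 takes intervention-related to mean the same as drug-related; if it does not, Table 5's cut-point is undefined. The all-AE and all-SAE tables, SAE oversight and the primary endpoint are not affected.

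**What to change.** Before database lock:

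1. In Example Table 5, separately for AEs and SAEs, count each patient once at the highest of the five causality levels. Give the related rate with its Wilson interval twice, with and without *unlikely*.
2. State in SAP 4.2 which of the two groupings is the headline, and why.
3. State that definitely unrelated AEs enter only the five-level table and the all-AE and all-SAE tables, and use one label, such as interruption-related, throughout.

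The first item is the substantive change; the other two are documentation. The cost is a few SAP sentences and some added rows in one table shell, several with very small counts at N = 32. No new data are needed, because Protocol 7.1 already has each AE recorded in the eCRF and "categorized in terms of severity, relationship to ARV interruption, outcome and seriousness".
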